The key secondary hypothesis is that the MQS predicts ADD better than the SICU optimal mobilization score [SOMS] (Schaller et al., 2016).

We also hypothesize that the MQS predicts ICU length of stay, hospital length of stay, functional independence measure (mmFIM) at ICU and hospital discharge, 3-month mortality, change in muscle mass quantified by change in RF-CSA, ICU coma- and delirium-free days, ICU ventilator-free days, ICU vasopressor-free days, ICU neuromuscular blocking agent free days, opioid dosage, corticosteroid days, and physical work capacity 3 months after hospital discharge quantified by the Duke Activity Status Index (DASI).

Covariate Data

Predefined confounders in multivariable adjusted analyses include APACHE2 (Knaus, Draper, Wagner, & Zimmerman, 1985), sex-adjusted rectus femoris cross sectional area (RFCSA) (Janssen, Heymsfield, Wang, & Ross, 2000) measured via bedside ultrasound upon admission, and the Risk Quantification Index for 30-day Postoperative Morbidity (PSS morbidity) (Dalton et al., 2011).

RFCSA measured by bedside ultrasound has been shown to be an independent predictor of adverse patient outcomes (Mueller, Eikermann 2016).

RFCSA will be adjusted for sex using published skeletal muscle mass values of the lower body of healthy adults (Janssen et al., 2000). Thus, RFCSA of female patients are multiplied with the coefficient 1.484, whereas male patients represent the reference group (adjustment coefficient 1). Sex-adjusted RFCSA will be used for further statistical analyses.

Statistical Analysis

All analyses are performed prospectively with prespecified endpoints and statistical methods.

Primary analysis

Unadjusted Analysis: We will conduct univariate logistic regression analysis to investigate the association between mobilization dose quantified by MQS and ADD.

Adjusted analysis: Multivariable logistic regression (mean daily mobilization dose (MQS)/ ADD) analyzing whether mobilization dose predicts adverse discharge independent from the defined covariates (APACHE2, PSS Morbidity score, and sex adjusted admission RFCSA).

Secondary analyses

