We will perform Net Reclassification Index and c-statistics to compare the predictive capability for ADD of the MQS to the SOMS. To further confirm the robustness of our results we will conduct Aikaike Information Criterion (AIC) and likelihood ratio test. AIC provides the relative quality of the estimated model. The likelihood ratio test compares the goodness of fit of two statistical models.

Multivariable logistic regression will be performed to evaluate the relationship between mean daily mobilization dose and other binary secondary outcomes controlling for above defined covariates. Zero truncated negative binomial regression will be used to analyze the association between mobilization dose and the secondary outcomes ICU and hospital length of stay. Negative binomial regression will be used to analyze the association between mobilization and the secondary outcomes coma- and delirium-free days, NMBA-free days, ventilator-free days, and functional independence measure (mmFIM) at ICU and Hospital discharge.

We will use linear regression to analyze the association between mobilization and physical work capacity 3 months after hospital discharge quantified by the Duke Activity Status Index (DASI) and opioids dosage (mg), if normality assumption is satisfied. Otherwise, transformation of the variables will be performed, and the transformed variables will be used as the outcome in the linear model.

Planned Sensitivity Analyses

Evaluation of confounder model: AUC-Analysis including the predefined confounders to determine the Area Under the receiver operator curve.

Categorized exposure variable: (2-quantile [high, low mobilization dose], tertiles [low, intermediate, high mobilization dose])

Alternative Exposure Variable: For each patient, mobilization data will be centered, and we will perform simple linear regression with the individual mean mobilization dose being the estimated intercept of each patient. The estimated slope from the linear regression will be considered as the change rate of mobilization dose. Two exposures will be included in our model, the slope of the mobilization dose and the intercept. We will conduct multivariable logistic analysis controlling for the same confounder variables (expected 4DoF: Intercept, Slope, APACHE2, RFCSA (continuous), PSS morbidity) from the primary analysis.

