Primary hypothesis

The primary hypothesis is that RFCSA is an independent predictor of mobilization dose in the SICU.

Statistical Analysis

All analyses are performed prospectively with prespecified endpoints and statistical methods.

We will conduct a generalized linear mixed effect model to analyze whether the RFCSA quantified via bedside ultrasound is an independent predictor of daily mobilization dose in the ICU.

Predefined confounders include the Barthel Index at hospital admission, APACHE2 and Charlson Comorbidity Index (CCI).

Secondary analysis

We will conduct a generalized linear mixed effect model to analyze whether the RFCSA quantified via bedside ultrasound is an independent predictor of daily mobilization dose in the ICU utilizing an alternative exposure variable. The exposure variable will be the binary variable "Sarcopenia

yes/no". Sarcopenia is quantified by RFCSA assessed through bedside ultrasound measurements within 48h. We will apply Youden's Index to define the optimal cutoff point of RFCSA for Sarcopenia. (Mueller, Eikermann 2016).

Sarcopenia is a clinical syndrome that describes progressive and generalized loss of skeletal muscle mass and strength and is associated with patient outcomes. (Delmonico, Harris, Lee, J Am Geriatr Soc, 2007)

Sample Size and Power

Based on data obtained by the same centers in the SOMS trial (Schaller et al., 2016) there is a correlation between mobilization dose and discharge disposition of 0.25. We therefore calculate that a sample size of 150 patients provides a power of >0.8 to identify a significant effect (alpha-error: 0.05) for our primary outcome.

Data collection

Data collection

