Date intubated, Date extubated, Reintubation (y/n)

ICU Discharge

mmFIM score in domains transfer and locomotion, ICU Discharge [date], ICU LOS, number of PT visits, ICU Readmission, weight at ICU discharge, medical interventions during ICU stay

Hospital Discharge

Hospital Discharge [date], Hospital Readmission, Hospital LOS, In-Hospital Mortality, Discharge destination, Total costs of care

Phone Call

DASI, Readmission to any Hospital, One-month mortality, Three-month mortality.

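### Negative binomial regression is planned for mmFIM, a function score; if the score's variance lies below its mean the test is very conservative and power may drop sharply

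*SAP*

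**What the plan says.** In section 2 of the SAP (Primary Aim, Secondary analyses) one sentence fixes the model for several outcomes: "Negative binomial regression will be used to analyze the association between mobilization and the secondary outcomes coma- and delirium-free days". It continues through NMBA-free and ventilator-free days and ends "and functional independence measure (mmFIM) at ICU and Hospital discharge".

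The Data collection section, under ICU Discharge, describes the variable as "mmFIM score in domains transfer and locomotion". The SAP states no range, number of levels, scoring rule, mean or variance for it.

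The only check of a model assumption with a fallback in Secondary analyses reads "if normality assumption is satisfied. Otherwise, transformation of the variables will be performed". It belongs to the linear models for DASI and opioid dose and does not reach mmFIM. The SAP also commits itself to methods fixed in advance, so changing the mmFIM model after seeing the data would depart from the plan.

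**The concern.** A score in transfer and locomotion grades function. It does not count events or days. The negative binomial variance is μ + αμ² with α ≥ 0, so it can represent variance equal to or above the mean, never below. It also has no upper limit.

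If mmFIM has variance below its mean, the estimate of α goes to zero, the fit becomes Poisson, and the model-based standard error reflects a variance larger than the data have. The test then rejects too rarely. A null result for mmFIM could come from the model and not from the data, and nothing in the plan would reveal this.

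**Working it through.** **Inputs from the SAP.** Sample Size and Power states that "a sample size of 150 patients provides a power of >0.8 to identify a significant effect (alpha-error: 0.05) for our primary outcome" and that "there is a correlation between mobilization dose and discharge disposition of 0.25". The adjusted model has three covariates: "defined covariates (APACHE2, PSS Morbidity score, and sex adjusted admission RFCSA").

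**Assumptions.** The test is two-sided (the SAP does not say). The 0.25 is borrowed as a latent correlation between dose and mmFIM; the SAP gives it for discharge disposition only. The mmFIM ranges (2–8, 0–8, 2–14, and 1–4 for a single domain) and the distribution shapes are also assumed.

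**Step 1: the plan's own figure.** By Fisher's z, power = Φ(atanh(0.25) × √147 − 1.96) = Φ(3.097 − 1.960) = Φ(1.137) = 0.87. This agrees with the stated power above 0.8 for the primary outcome.

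**Step 2: can the variance exceed the mean?** On a scale from a to b with mean m, the variance is at most (m − a)(b − m). The largest possible variance/mean ratio is therefore a + b − m − ab/m at a given m, and (√b − √a)² over all m.
- Single domain 1–4: (2 − 1)² = 1, so overdispersion is impossible.
- Sum 2–8: 10 − 2√16 = 2, so overdispersion is possible.
- Sum 2–14: 16 − 2√28 = 5.4, so overdispersion is possible.

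The range alone does not settle the matter; the shape matters too.

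**Step 3: size of the effect by formula.** With φ = variance/mean below 1, the Poisson standard error is too wide by 1/√φ. Power is then about Φ(atanh(r) × √147 − 1.96/√φ). For the 2–8 ceiling shape below, φ = 0.43 and the observed correlation is 0.23, so power ≈ Φ(2.839 − 2.989) = Φ(−0.150) = 0.44. The rejection rate under the null is 2 × (1 − Φ(2.989)) ≈ 0.003.

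**Step 4: simulation against linear regression.** n = 150, latent correlation 0.25, three covariates, 400 runs per case (simulation error about 2.5 points).

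| Assumed scale, shape | Variance/mean | Negative binomial | Linear |
|---|---|---|---|
| 2–8 bell | 0.45 | 0.52 | 0.87 |
| 2–8 ceiling | 0.43 | 0.43 | 0.80 |
| 2–14 ceiling | 0.43 | 0.37 | 0.79 |
| 0–8 ceiling | 0.62 | 0.60 | 0.81 |
| 2–8 uniform | 0.80 | 0.76 | 0.83 |
| 2–14 bell | 1.05 | 0.87 | 0.88 |
| 2–8 U-shaped | 1.13 | 0.83 | 0.82 |
| 0–8 uniform | 1.67 | 0.80 | 0.82 |
| 2–14 uniform | 1.75 | 0.82 | 0.82 |
| 0–8 U-shaped | 2.35 | 0.72 | 0.82 |

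Under the null, the negative binomial test rejected in 0.000 to 0.007 of runs for the 2–8 bell and the ceiling shapes. In the 2–8 bell, uniform and ceiling cases α was zero in every run. Poisson regression with robust standard errors gave power of 0.81, 0.84 and 0.79 for the 2–8, 0–8 and 2–14 ceilings.

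**Step 5: simulation against proportional odds.**

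| Case | Runs, covariates | Negative binomial | Proportional odds |
|---|---|---|---|
| 2–8 bell | 200, three | 0.61 | 0.86 |
| 2–8 ceiling | 200, three | 0.39 | 0.85 |
| 2–8 bell | 100, none | 0.58 | 0.87 |
| 2–8 ceiling | 100, none | 0.30 | 0.84 |
| 2–14 ceiling | 100, none | 0.59 | 0.87 |
| 2–8 U-shaped | 100, none | 0.80 | 0.81 |
| 2–14 uniform | 100, none | 0.85 | 0.89 |

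In the 100-run cases robust Poisson gave 0.79 to 0.89, matching proportional odds throughout. For the 2–14 ceiling, 0.37 in Step 4 and 0.59 here differ by more than simulation error, so the loss should be read as a range.

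**The case against.** The strongest reply is that the SAP never gives mmFIM's range or variance, so underdispersion is a supposition. A reader might infer that mmFIM has low variance and that its standard errors will be wrong. The documents do not support that. A bounded score can be overdispersed, and the U-shaped 2–8 and uniform 2–14 cases show almost no loss. This part of the objection stands, and the conclusion must be conditional.

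A reader might also infer that a short scale loses power and a long one does not. The 2–14 ceiling case contradicts this, as does the U-shaped 2–8 case.

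A third tempting reading is that proportional odds can never do worse. The simulations above generate scores from a latent variable, which is close to that model's own assumption. In a constructed example on 2–14, where dose changes only the chance of the top score (variance/mean 2.9), power was 0.84 for negative binomial, 0.79 for robust Poisson and 0.41 for proportional odds. This is an illustration and not a forecast, but it rules out a claim of uniform superiority.

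Finally, mmFIM is one item in a long list of further hypotheses. The SAP's key secondary hypothesis compares MQS with SOMS for adverse discharge, so mmFIM should not be presented as a leading secondary outcome.

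What the objection does not remove is that the model was written down for an outcome of another type, without any safeguard.

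**Conclusion.** The point holds in conditional form. The mismatch between an unbounded count model and a function score is in the text and needs no simulation. The size of the harm does depend on the assumed scale, shape and effect.

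If variance is well below the mean (ratio about 0.43 to 0.45), negative binomial power is roughly 0.3 to 0.6 where an ordinal model has about 0.85, and the null rejection rate is far below 5%. At ratios of 0.6 to 0.8 the loss is smaller. Above 1 there is mostly little or none; the exception seen was a U-shaped 0–8 score (0.72 against 0.82 for linear regression), where low variance is not the cause.

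Under underdispersion the error is towards missed associations, not false positives. It affects mmFIM at ICU and hospital discharge only and leaves the primary analysis, its sample size and its power statement as they are. This is a worthwhile improvement, not a threat to the trial's main conclusion.

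**What to change.** Take mmFIM out of the negative binomial sentence and state its range and how the two domains are combined. For mmFIM at ICU and at hospital discharge, specify one of two equally acceptable models with the same three covariates:

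- proportional-odds regression, with a check of the proportional-odds assumption; or
- a log-link mean model (Poisson) with robust standard errors.

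The cost is SAP wording; no new data, patients or visits are needed. With proportional odds, the effect becomes an odds ratio and rests on proportionality. With robust Poisson, the ratio of mean scores is kept, but the test may be slightly liberal at this sample size: null rejection ran from 0.043 to 0.075 over the 2–8 ceiling and U-shapes and all 0–8 and 2–14 shapes tried (400 runs each, simulation error √(0.05 × 0.95/400) = 1.1 points).

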Statistical Analysis Plan

Effects of mobilization dose in surgical intensive care unit patients on adverse discharge disposition

Original Date: August, 20, 2018

Table of Contents

1. Primary and Secondary Aim Overview.....	2
2. Primary aim.....	2
Hypotheses.....	2
Covariate Data.....	3
Statistical analysis.....	3
3. Secondary aim.....	5
Hypothesis.....	5
Statistical Analysis.....	5
4. Sample Size.....	6
5. Data collection.....	6

1. Primary and Secondary Aim Overview

Primary Aim

The primary aim of this study is to assess the effects of mobilization dose in critically ill patients on adverse discharge disposition (ADD) (primary outcome). The primary hypothesis of this study is that the mobilization dose in the surgical intensive care unit measured by Mobilization Quantification Score (MQS) is associated with ADD.

Secondary Aim

The secondary aim is to evaluate the association between rectus femoris cross sectional area (RFCSA) measured by bedside ultrasound within 48 hours of enrollment and mobilization dose received in the surgical intensive care unit (SICU).

2. Primary Aim

This study aim is driven by the research hypothesis that the MQS - a new method to quantify mobilization dose based on intensity and duration with more granularity than currently used mobilization quantification instruments - reflects the improving effects of early mobilization on discharge disposition.

Exposure variable

The primary exposure variable is the mean daily mobilization dose quantified by the MQS. The MQS is a newly developed score that quantifies mobilization provided by SICU nurses and physical therapists incorporating the mobilization level as well as its duration. The MQS is calculated daily throughout the SICU stay and will be divided by the number of ICU days to arrive at the exposure variable mean daily mobilization dose.

The secondary exposure variable used for comparison is the SICU optimal mobilization score (SOMS).

Primary Outcome

The primary outcome ADD is defined as discharge to facilities providing long-term care assistance for daily activities, including nursing homes and skilled nursing facilities, hospice at the patient's home, hospice in a healthcare facility, or in-hospital mortality.

Hypotheses

Primary Hypothesis

The primary hypothesis is that mobilization dose quantified via MQS predicts adverse discharge disposition.

Secondary Hypothesis

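### The shape of the MQS effect on ADD is checked only by a median split and tertiles, so if benefit flattens with dose the single odds ratio is too weak at low dose and too strong at high dose

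*SAP*

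**What the plan says.** Section 2 of the SAP defines the exposure: "The primary exposure variable is the mean daily mobilization dose quantified by the MQS". The primary analysis has two parts. Unadjusted: "We will conduct univariate logistic regression analysis to investigate the association between mobilization dose quantified by MQS and ADD". Adjusted: "Multivariable logistic regression (mean daily mobilization dose (MQS)/ ADD) analyzing whether mobilization dose predicts adverse discharge independent from the defined covariates", the covariates being APACHE2, PSS morbidity and sex-adjusted admission RFCSA.

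No transformation, spline, polynomial or linearity check is given for MQS. The SAP does not say that the term is linear; that is inferred. Categorised MQS appears separately under Planned Sensitivity Analyses ("Categorized exposure variable: (2-quantile [high, low mobilization dose], tertiles [low, intermediate, high mobilization dose"), so the primary model must use MQS ungrouped. The term list for the intercept/slope model also names each variable once ("expected 4DoF: Intercept, Slope, APACHE2, RFCSA (continuous), PSS morbidity"). The categorised analysis has no test, contrast or reporting rule attached.

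**The concern.** The study question is about dose, and the SAP justifies MQS by its finer grain compared with existing instruments. A single linear term yields one odds ratio per unit, taken to hold across the whole dose range. If the step from little to some mobilization matters more than further increases, that odds ratio is an average that fits neither end: too close to 1 at low dose and too far from 1 at high dose. A reader would be told that benefit continues where it has stopped, and that the first step up is worth less than it is. The planned categorical analysis discards the granularity that would reveal this.

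**Working it through.** **1. The plan's own figure.** From Sample Size and Power: r = 0.25, N = 150, alpha 0.05 (two-sided assumed). With the Fisher z test,

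power = Φ(atanh(0.25) × √147 − 1.960) = Φ(0.2554 × 12.124 − 1.960) = Φ(1.137) = 0.872.

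N for 80% power = 3 + ((1.960 + 0.842)/0.2554)² ≈ 123.3, so 124. The stated power above 0.8 is reproduced.

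**2. Does any other planned analysis address the shape?**
- AIC and the likelihood ratio test accompany the MQS-versus-SOMS comparison.
- The intercept/slope model concerns change over the ICU stay ("The estimated slope from the linear regression will be considered as the change rate of mobilization dose"), not the curve of ADD against dose.
- The transformation rule is for outcomes of the linear models, DASI and opioid dose ("the transformed variables will be used as the outcome in the linear model").
- The propensity score analysis uses a high/low split of MQS.

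Only the categorised exposure remains.

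**3. Size of the distortion under a plateau.** Assumed truth: logit P(ADD) = a + b × min(MQS, k), scaled so that MQS and ADD correlate at −0.25 (the SAP's 0.25, in the direction of benefit). The SAP gives no MQS distribution, ADD rate or plateau. These were therefore varied: MQS gamma (shape 2) or normal, ADD 30% or 50%, k at the median or the 67th percentile.

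| MQS | Plateau from | True OR per SD below | True OR above | Straight-line OR per SD |
|---|---|---|---|---|
| gamma | median | about 0.10 | 1.00 | 0.49–0.57 |
| gamma | 67th percentile | 0.24–0.27 | 1.00 | 0.48–0.57 |
| normal | median | 0.32–0.35 | 1.00 | 0.56–0.59 |
| normal | 67th percentile | 0.45 | 1.00 | 0.56–0.59 |

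**4. The same as dose contrasts, plateau at the median.** OR for a contrast = (OR per SD) raised to the distance in SD.

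Gamma (shape 2): P10, P50 and P90 are 0.532, 1.678 and 3.890, and the SD is 1.414. P10 to P50 is therefore 0.81 SD and P50 to P90 is 1.56 SD.
- Truth: 0.10^0.81 = 0.15, then 1.00.
- Straight line: 0.49^0.81 = 0.56 to 0.57^0.81 = 0.63, then 0.49^1.56 = 0.33 to 0.57^1.56 = 0.42.
- Direct simulation at N = 150 agrees closely: truth 0.16 and 1.00; straight line 0.54–0.62 and 0.31–0.40; 3-knot spline 0.23–0.24 and 0.60–0.64.

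Normal: both distances are 1.28 SD.
- Truth: 0.32^1.28 = 0.23 to 0.35^1.28 = 0.26, then 1.00.
- Straight line: 0.56^1.28 = 0.48 to 0.59^1.28 = 0.51 for both contrasts.

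**5. What the planned tertiles would show (50 patients each).** With gamma MQS and a plateau at the median, the ORs for middle versus low and high versus middle are about 0.26 and 0.80. With no plateau they are 0.60–0.68 and 0.42–0.49. The point estimates do hint at an early plateau. Power of a tertile contrast for non-linearity, which the SAP does not specify, against the spline's 1-df likelihood ratio test:

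| Plateau from (gamma MQS) | Tertile contrast | Spline |
|---|---|---|
| median | 25–34% | about 72–82% |
| 67th percentile | 6–7% | about 40–51% |
| none (false positives) | 7% | about 3–6% |

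With normal MQS the tertile contrast reaches 19–25% and 9–10% for the two plateaus.

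**6. The primary test.** With the correlation held at 0.25, the linear test has about 84–92% power under these plateaus.

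**The case against.** The SAP's hypothesis is that MQS is associated with, and predicts, ADD. It claims no particular dose-response shape, and a linear term tests that hypothesis validly. This stands: there is no misstatement or contradiction here, only a weak choice of sensitivity analysis.

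A reader might infer that the linear test loses power under a plateau. The documents do not support that. The SAP plans on "there is a correlation between mobilization dose and discharge disposition of 0.25", and with that held fixed the test stays above 80%. Power falls clearly only if the effect is also assumed weaker than planned. When the effect is truly linear, the 2-df spline test is the weaker one (83–92% against 90–95%), which is a reason to leave the primary test alone.

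Nor would the single odds ratio be the only thing reported. In simulated data with an early plateau, tertiles show the steeper first step in 89–99% of replicates. But they show it in 25–40% when the effect is linear, so the pattern alone is not decisive, and a plateau starting near or inside the top tertile is largely hidden.

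Skewness, and the plateau itself, are assumptions. With normal MQS the distortion shrinks but keeps its direction.

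It is also tempting to let a significant non-linearity test decide which odds ratio is reported. That would make reporting data-driven and would usually miss gentle saturation, which was detected in only about 10–25% of simulated trials.

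**Conclusion.** The point holds as a cheap and worthwhile improvement to the sensitivity analysis. The primary test and the sample size are unaffected. If benefit flattens with dose, the single odds ratio understates the effect at low dose and overstates it at high dose; the planned median split cannot reveal this and the tertiles do so only informally. The error is large for a plateau at the median with skewed MQS, and moderate with normal MQS or a later plateau. It is absent if the effect is linear. All sizes depend on the assumed MQS distribution, ADD rate and plateau position, and the reading of the primary model as linear is inferred from its structure. The SAP gives no evidence that a plateau exists, and none should be read into this point.

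**What to change.** State in the SAP that mean daily MQS enters the primary model as a linear term, and keep that as the prespecified test and estimate. Replace the median-split sensitivity analysis by a restricted cubic spline for mean daily MQS with 3 knots, at the 10th, 50th and 90th percentiles, in the same adjusted model. Always report the spline odds ratios from P10 to P50 and from P50 to P90, with confidence intervals, beside the linear odds ratio. Give the likelihood ratio test of the non-linear term as supporting information, not as a switch for what is reported. Tertiles may stay as description.

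Cost: some SAP wording and one further model with one extra degree of freedom; no new data. The spline contrasts will have wider intervals. Some bias remains under a sharp plateau (0.23–0.24 against a true 0.16, and 0.60–0.64 against 1.00, in the gamma case), and 150 patients give limited power to detect mild curvature.

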Evaluate the AUC with alternative Exposure Variable (intercept/ slope): We will compare discriminative ability of our primary model to a model with two exposure variables (intercept (mean mobilization dose for each patient) and slope) utilizing Net Reclassification Index, Brier Score and c-statistics.

Generalized propensity score: In an exploratory approach, accounting for the degrees of freedom available, we will include a generalized propensity score to reduce bias induced by discrepancies in patient characteristics. The propensity score will be generated from different covariates identified as influencing the exposure including APACHE, GCS at enrollment, ASA at admission, PSS-Morbidity, duration of ventilation, duration of sedation, duration of delirium, opioid dose, vasopressors. The propensity score will be confined for a binary exposure variable. To derive at a binary variable, we will categorize the mean mobilization dose (MQS) into two categories, high vs. low.

Subgroup analyses: We will perform a subgroup analysis in patients who received surgery upon admission to the ICU.

Planned Exploratory Analyses

We aim to explore the association of other variables that can be used to quantify mobilization intensity and duration (other than the composite exposure MQS) and adverse discharge disposition.

The additional variables used to quantify mobilization intensity and/or dose are:

- Mean highest achieved level of mobilization therapy (Daily highest achieved ICU mobilization scale level/ICU days)
- Highest achieved mobilization level using ICU mobilization score
- Mean number of daily mobilization sessions (Total number of mobilization units/ICU days)
- Mean duration of mobilization units according to MQS (Total duration of mobilization treatment based on MQS/number of sessions throughout the ICU stay)
- Fraction of days mobilized (Number of mobilization days/ ICU days)
- Early mobilization frequency (Total number of mobilization units from day 1 through 3 on the ICU)

We will use multivariable logistic regression for exploratory analyses analyzing the association between the above-mentioned variables used to quantify mobilization intensity and/or dose.

3. Secondary Aim

Exposure variable

The RFCSA assessed through bedside ultrasound measurements within 48h is used as a continuous exposure variable.

Outcomes

The outcome for the secondary aim of the study is the repeatedly measured daily mobilization dose as quantified by the MQS.

Hypothesis

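### The comparison of the primary model with the mean-plus-slope model uses uncorrected NRI, Brier score and c-statistic, which lean slightly to the larger model when the slope is noise

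*SAP*

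**What the plan says.** All of this stands in SAP section 2 unless noted.

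- **Primary analysis.** The adjusted logistic model relates mean daily MQS dose to ADD, "independent from the defined covariates (APACHE2, PSS Morbidity score, and sex adjusted admission RFCSA").
- **Planned Sensitivity Analyses, alternative exposure.** A line is fitted to each patient's daily doses, "with the individual mean mobilization dose being the estimated intercept of each patient". Then: "Two exposures will be included in our model, the slope of the mobilization dose and the intercept". The confounders stay the same.
- **Planned Sensitivity Analyses, AUC with the alternative exposure.** "We will compare discriminative ability of our primary model to a model with two exposure variables", namely intercept and slope, "utilizing Net Reclassification Index, Brier Score and c-statistics".
- **Secondary analyses.** AIC and the likelihood ratio test are named, but only for MQS against SOMS.
- **Sample Size and Power.** One cohort: "a sample size of 150 patients provides a power of >0.8 to identify a significant effect (alpha-error: 0.05").

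For the slope comparison the SAP names no validation sample, cross-validation, bootstrap or optimism correction. It does not say which NRI is meant, and it sets no criterion for calling one model better.

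**The concern.** By the SAP's own definition the intercept is the patient's mean dose, which is the primary exposure. The two models are therefore nested and differ by one parameter. An added parameter can only raise the maximised likelihood in the data used for fitting. The Brier score, c-statistic and NRI need not follow in every data set, but they tend to. Read without correction, their point estimates then contain some gain that comes from fitting alone. At stake is whether the rate of change of dose is described as adding to mean dose when it may not.

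**Working it through.** **1. The plan's own figure.** Inputs from Sample Size and Power: "there is a correlation between mobilization dose and discharge disposition of 0.25", N = 150, alpha 0.05 with sidedness not stated. By Fisher's z, power = Φ(atanh(0.25)·√(150 − 3) − 1.96) = Φ(0.2554 × 12.124 − 1.96) = Φ(1.137) = 0.872 two-sided. A noncentral t calculation gives 0.881, and one-sided Fisher z gives 0.927. All agree with the stated power above 0.8. This confirms N and alpha as read; it does not bear on the slope comparison.

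**2. The two models.**

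- A: logit P(ADD) = β0 + β1·mean dose + β2·APACHE2 + β3·PSS morbidity + β4·RFCSA
- B: A + β5·slope

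A is B with β5 = 0.

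**3. The measures.** With p the predicted probability and y the outcome:

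- Δc = c(B) − c(A), where c is the share of ADD/non-ADD pairs ranked correctly
- ΔBrier = mean (y − p_B)² − mean (y − p_A)²; negative favours B
- category-free NRI = [P(up) − P(down)] among ADD patients − [P(up) − P(down)] among the others, where up means p_B > p_A
- likelihood ratio statistic = 2(ℓ_B − ℓ_A), referred to chi-squared on 1 df; reject above 1.96² = 3.84

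**4. Simulation with a noise slope.** 2,000 data sets of 150 patients per scenario, true β5 = 0, both models fitted and scored on the same patients. These assumptions are not in the SAP: ADD rate 0.20, 0.35 or 0.50; independent standard-normal predictors; dose log-OR −0.55 per SD; covariate log-ORs of size 0.2, 0.4 or 0.7 per SD; three-category NRI cut at 1/3 and 2/3.

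| ADD rate | Covariate log-OR | c of A | c higher | mean Δc | Brier lower | mean ΔBrier | category-free NRI > 0 | mean NRI | 3-category NRI > 0 | LRT rejects |
|---|---|---|---|---|---|---|---|---|---|---|
| 0.20 | 0.4 | 0.742 | 74.3% | +0.0069 | 80.7% | −0.00121 | 80.8% | +0.149 | 52.1% | 5.9% |
| 0.35 | 0.4 | 0.735 | 74.6% | +0.0048 | 87.9% | −0.00140 | 80.7% | +0.125 | 55.4% | 5.1% |
| 0.50 | 0.4 | 0.733 | 73.6% | +0.0043 | 89.7% | −0.00145 | 80.2% | +0.118 | 55.6% | 5.4% |
| 0.35 | 0.7 | 0.803 | 72.1% | +0.0035 | 83.7% | −0.00138 | 82.4% | +0.137 | 53.5% | 6.1% |
| 0.35 | 0.2 | 0.689 | 73.0% | +0.0059 | 89.2% | −0.00137 | 80.7% | +0.116 | 55.7% | 4.4% |

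The Monte Carlo standard error of a 5% rejection rate is √(0.05 × 0.95/2000) = 0.5 percentage points. Further runs under other assumptions (ADD about 20–50%) moved the ranges little: Brier lower in up to 92%, category-free NRI positive in as few as 78% with mean down to +0.11, likelihood ratio test rejecting in 5–7%. Letting the slope correlate 0.4 with mean dose did not change the picture.

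**5. The same fits in new patients.** Scored on 3,000 new patients, B had the higher c-statistic in only 15–20% of data sets (mean −0.003 to −0.006) and the lower Brier score in only 15–17% (mean +0.0014 to +0.0016). The in-sample lean is therefore optimism.

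**6. If the differences are tested.**

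- A z-test on the category-free NRI rejects in about 6–9%. In a run split by direction, 6.0–7.6% of data sets rejected in favour of B and at most 0.05% against it.
- A paired DeLong test of the c-statistic significantly favours B in 0–0.3%.
- A paired z-test of the Brier difference does so in 0–0.15%.

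**The case against.** The strongest reply is that little follows from this. The mean gain in c-statistic is about 0.005. At two decimals the c-statistic is higher in only 30–46% of noise data sets, and it actually falls in 22–24%. All three indices (with the category-free NRI) favour the larger model together in only 53–60%. The alternative-exposure model already estimates the slope's coefficient, and its Wald test rejects in 4.1–5.3% under the null, so a reader need not rely on the indices. All of this stands, and it limits the point to a small lean.

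Three stronger readings are tempting and are not supported:

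- *The comparison will generally announce an improvement whether or not the slope matters.* That needs a rule under which any difference above zero counts as better. The SAP only says that discriminative ability will be compared. If the c-statistic or Brier differences were tested in pairs, the procedure would be very conservative.
- *The NRI nearly triples the false-positive rate.* This sets about 7% against 2.5%, because the rejections fall on one side. The SAP states alpha 0.05 without sidedness and plans no NRI test in so many words. Against a two-sided 5% the excess is about 1 to 4 percentage points. It also applies only to the category-free version, which the SAP does not specify.
- *The indices are the only basis for judging the slope.* The SAP does not say so.

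What the reply does not remove is that no test of the slope is tied to this comparison, and nothing in the plan separates a gain of this size from chance.

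**Conclusion.** The point holds in a narrow form. Three indices are to be compared between nested models in one cohort, with no optimism correction named, and for a noise slope the c-statistic, Brier score and category-free NRI lean to the larger model in roughly three quarters to nine tenths of data sets. The lean is small in absolute terms, and much weaker for a three-category NRI.

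That both models are scored on the fitting data is inferred from the single cohort and the absence of any validation step; the SAP does not state it. The percentages rest on assumed ADD rates and covariate effects, but the direction was the same in all five tabulated scenarios. Nesting rests on the SAP's statement that the intercept is the individual mean dose.

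The primary logistic regression and the MQS–SOMS comparison are not affected. This is a cheap improvement, not a flaw that threatens the trial's conclusion.

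**What to change.** In the paragraph on the AUC with the alternative exposure:

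1. Judge the added value of the slope by the 1-df likelihood ratio test. The method is already in the SAP for MQS against SOMS and would be assigned here as well.
2. Fit both models to the same patients, namely those with enough ICU days for a slope to be estimated. A single day gives no slope, and likelihoods from different patient sets cannot be compared. State how many patients this leaves out.
3. Report the c-statistic and Brier differences after bootstrap optimism correction: resample patients, refit both models in each resample, score them in the resample and in the original data, and subtract the average excess.
4. Do not use the NRI as evidence of improvement. If it is kept as description, say which version it is.

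The cost is a few lines of SAP wording and a bootstrap loop, with no new data. The reported gain will be slightly smaller, and the mean-only model must be refitted in the reduced set, so its estimates may differ a little from the primary analysis.
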